6.2 Recording of Adverse Events

At each contact with the subject, the investigator must seek information on adverse events by specific questioning and, as appropriate, by examination. Information on all adverse events should be recorded immediately in the source document, and also in the appropriate adverse event module of the case report form (CRF). All clearly related signs, symptoms, and abnormal diagnostic procedures results should be recorded in the source document, though should be grouped under one diagnosis.

All adverse events occurring during the study period must be recorded. The clinical course of each event should be followed until resolution, stabilization, or until it has been determined that the study treatment or participation is not the cause. Serious adverse events that are still ongoing at the end of the study period must be followed up to determine the final outcome. Any serious adverse event that occurs after the study period and is considered to be possibly related to the study treatment or study participation should be recorded and reported immediately.

6.3 Reporting of Serious Adverse Events and Unanticipated Problems

Investigators and the protocol sponsor must conform to the adverse event reporting timelines, formats and requirements of the various entities to which they are responsible, but at a minimum those events that must be reported are those that are:

- related to study participation,

CONFIDENTIAL

This material is the property of the NYU School of Medicine and Langone Medical Center. Do not disclose or use except as authorized in writing by the study sponsor

- unexpected, and
- serious or involve risks to subjects or others

For Narrative Reports of Safety Events

If the report is supplied as a narrative, the minimum necessary information to be provided at the time of the initial report includes:

- | | |
|---|--|
| 
• Study identifier• Study Center• Subject number• A description of the event• Date of onset | 
• Current status• Whether study treatment was discontinued• The reason why the event is classified as serious• Investigator assessment of the association between the event and study treatment |
|---|--|

6.3.1 Investigator reporting: notifying the IRB

Federal regulations require timely reporting by investigators to their local IRB of unanticipated problems posing risks to subjects or others. The following describes the NYULMC IRB reporting requirements, though Investigators at participating sites are responsible for meeting the specific requirements of their IRB of record.

Report Promptly, but no later than 5 working days:

Researchers are required to submit reports of the following problems promptly but no later than 5 working days from the time the investigator becomes aware of the event:

- ***Unanticipated problems including adverse events that are unexpected and related***
 - *Unexpected: An event is “unexpected” when its specificity and severity are not accurately reflected in the protocol-related documents, such as the IRB-approved research protocol, any applicable investigator brochure, and the current IRB-approved informed consent document and other relevant sources of information, such as product labeling and package inserts.*
 - *Related to the research procedures: An event is related to the research procedures if in the opinion of the principal investigator or sponsor, the event was more likely than not to be caused by the research procedures.*
 - *Harmful: either caused harm to subjects or others, or placed them at increased risk*

Other Reportable events:

The following events also require prompt reporting to the IRB, though **no later than 5 working days**:

- **Complaint of a research subject** when the complaint indicates unexpected risks or the complaint cannot be resolved by the research team.

CONFIDENTIAL

This material is the property of the NYU School of Medicine and Langone Medical Center. Do not disclose or use except as authorized in writing by the study sponsor

- **Protocol deviations or violations** (includes intentional and accidental/unintentional deviations from the IRB approved protocol for any of the following situations:
 - *one or more participants were placed at increased risk of harm*
 - *the event has the potential to occur again*
 - *the deviation was necessary to protect a subject from immediate harm*
- **Breach of confidentiality**
- **Incarceration of a participant** when the research was not previously approved under Subpart C and the investigator believes it is in the best interest of the subject to remain on the study.
- **New Information indicating a change to the risks or potential benefits** of the research, in terms of severity or frequency. (e.g. analysis indicates lower-than-expected response rate or a more severe or frequent side effect; Other research finds arm of study has no therapeutic value; FDA labeling change or withdrawal from market)

Reporting Process

The reportable events noted above will be reported to the IRB using the form: “Reportable Event Form” or as a written report of the event (including a description of the event with information regarding its fulfillment of the above criteria, follow-up/resolution and need for revision to consent form and/or other study documentation).

Copies of each report and documentation of IRB notification and receipt will be kept in the Clinical Investigator’s study file.

Data and Safety Monitoring Plan

7 Data Handling and Record Keeping

7.1 Confidentiality

While PHI will temporarily be seen, none will be collected, stored, or recorded for this study. All de-identified data will be stored securely. The database will be stored securely in a password-protected electronic spreadsheet and only accessible to those individuals granted access to it by the research staff. No other individuals beyond those identified within the study protocol will be permitted to view, handle, or possess the data. The research data will be de-identified to protect confidentiality. No PHI will be recorded.

7.2 Confidentiality and HIPAA

Information about study subjects will be kept confidential and managed according to the requirements of the Health Insurance Portability and Accountability Act of 1996 (HIPAA). Those regulations require a signed subject authorization informing the subject of the following:

CONFIDENTIAL

This material is the property of the NYU School of Medicine and Langone Medical Center. Do not disclose or use except as authorized in writing by the study sponsor

- What protected health information (PHI) will be collected from subjects in this study
- Who will have access to that information and why
- Who will use or disclose that information
- The rights of a research subject to revoke their authorization for use of their PHI.

In the event that a subject revokes authorization to collect or use PHI, the investigator, by regulation, retains the ability to use all information collected prior to the revocation of subject authorization. For subjects that have revoked authorization to collect or use PHI, attempts should be made to obtain permission to collect at least vital status (i.e. that the subject is alive) at the end of their scheduled study period.

7.3 Source Documents

Source data is all information, original records of clinical findings, observations, or other activities in a clinical trial necessary for the reconstruction and evaluation of the trial. Source data are contained in source documents. Examples of these original documents, and data records include: hospital records, clinical and office charts, laboratory notes, memoranda, subjects' diaries or evaluation checklists, pharmacy dispensing records, recorded data from automated instruments, copies or transcriptions certified after verification as being accurate and complete, microfiches, photographic negatives, microfilm or magnetic media, x-rays, subject files, and records kept at the pharmacy, at the laboratories, and at medico-technical departments involved in the clinical trial.

7.4 Case Report Forms

The study case report form (CRF) is the primary data collection instrument for the study. All data requested on the CRF must be recorded. All missing data must be explained. If a space on the CRF is left blank because the procedure was not done or the question was not asked, write "N/D". If the item is not applicable to the individual case, write "N/A". All entries should be printed legibly in black ink. If any entry error has been made, to correct such an error, draw a single straight line through the incorrect entry and enter the correct data above it. All such changes must be initialed and dated. DO NOT ERASE OR WHITE OUT ERRORS. For clarification of illegible or uncertain entries, print the clarification above the item, then initial and date it.

7.5 Records Retention

The Principal Investigator and other researchers must ensure that all Research Data is maintained in accordance with this Policy for the longer of (i) three (3) years after the final project close-out or (ii) six (6) years after any reporting, publication, presentation, or use in any grant application by the researcher of such Research Data, or self-citation of the same in such manner that may be of benefit to such researcher.

CONFIDENTIAL

This material is the property of the NYU School of Medicine and Langone Medical Center. Do not disclose or use except as authorized in writing by the study sponsor

8 Data and Safety Monitoring Plan

8.1 Data and Study Monitoring Plan

The Investigator will allocate adequate time to monitor the activities of the study. The Investigator will ensure that the monitor or other compliance or quality assurance reviewer is given access to all the above noted study-related documents and study related facilities (e.g. pharmacy, diagnostic laboratory, etc.), and has adequate space to conduct the monitoring visit. The Investigator is able to stop the study whenever they see fit. However, this is not anticipated as the level of safety associated with the study has minimal to no differences in risk compared to the normal standard of care. Written reports will be submitted to the IRB if any concerns regarding the monitoring plan arise. To further ensure safety, the other study members will monitor the participants on an ongoing basis. Each member will be trained in the definition, monitoring, and reporting of adverse events, as well as both anticipated and unanticipated problems.

Study data and safety monitoring will focus on several areas and will be periodically reviewed to ensure that the study is meeting study expectations. These areas will be reviewed biweekly:

- Safety – to assess the mechanisms used to protect the safety and privacy of the study participants as well as the extent and magnitude of adverse events.
- Performance – to assess performance with respect to participant recruitment, retention, and follow-up, Case Report Form (CRF) tracking, protocol adherence, and quality of data
- Intervention effects – to assess whether the study should continue based on safety and efficacy data (if applicable).

8.2 Auditing and Inspecting

The investigator will permit study-related monitoring, audits as frequently as necessary, and inspections by the IRB, the sponsor, government regulatory bodies, and University compliance and quality assurance groups of all study related documents (e.g. source documents, regulatory documents, data collection instruments, study data etc.). The investigator will ensure the capability for inspections of applicable study-related facilities (e.g. pharmacy, diagnostic laboratory, etc.). Written reports will be submitted to the IRB if any concerns regarding auditing and/or inspection arise.

Participation as an investigator in this study implies acceptance of potential inspection by government regulatory authorities and applicable University compliance and quality assurance offices.

9 Ethical Considerations

CONFIDENTIAL

This material is the property of the NYU School of Medicine and Langone Medical Center. Do not disclose or use except as authorized in writing by the study sponsor

This study is to be conducted accordance with applicable US government regulations and international standards of Good Clinical Practice, and applicable institutional research policies and procedures.

This protocol and any amendments will be submitted to a properly constituted Institutional Review Board (IRB) in agreement with local legal prescriptions, for formal approval of the study conduct. The decision of the IRB concerning the conduct of the study will be made in writing to the investigator and a copy of this decision will be provided to the sponsor before commencement of this study. The investigator should provide a list of IRB members and their affiliate to the sponsor.

All subjects for this study will be provided a consent form describing this study and providing sufficient information for subjects to make an informed decision about their participation in this study. This consent form will be submitted with the protocol for review and approval by the IRB for the study. The formal consent of a subject, using the IRB-approved consent form, must be obtained before that subject undergoes any study procedure. The consent form must be signed by the subject or legally acceptable surrogate, and the investigator-designated research professional obtaining the consent.

In addition, it will describe who will obtain consent and how the process of informed consent will be structured to be conducive to rational and thoughtful decision making by the subject/subject's legally authorized representative. If children and/ or cognitively impaired adults will be subjects, include a specific plan to assess comprehension during assent or the subject's agreement. Individuals who are authorized to obtain consent must be listed on the protocol (or FDA form 1572) and consent form document. If necessary to use 'Auditor/Witness' and/or translator, these roles would be described in this section.

Include a plan for assessing subject capacity in cognitively impaired subjects. Describe the anticipated degree of impairment relative to their ability to consent and the anticipated direct benefits to the subjects.

10 Study Finances

10.1 *Conflict of Interest*

Any investigator who has a conflict of interest with this study (patent ownership, royalties, or financial gain greater than the minimum allowable by their institution, etc.) must have the conflict reviewed by a properly constituted Conflict of Interest Committee with a Committee-sanctioned conflict management plan that has been reviewed and approved by the study sponsor prior to participation in this study. All NYULMC investigators will follow the applicable University conflict of interest policies.

CONFIDENTIAL

This material is the property of the NYU School of Medicine and Langone Medical Center. Do not disclose or use except as authorized in writing by the study sponsor

10.2 Costs and payments

Patients will not be financially reimbursed throughout this study. Also, there will be no funding necessary for this study as all three wound closure techniques are currently and regularly in use at the institution and there are no supply cost differences between them.

11 Publication Plan

Neither the complete nor any part of the results of the study carried out under this protocol, nor any of the information provided by the sponsor for the purposes of performing the study, will be published or passed on to any third party without the consent of the study sponsor. Any investigator involved with this study is obligated to provide the sponsor with complete test results and all data derived from the study.

12 References

1. Iorio, R., et al., *Early Results of Medicare's Bundled Payment Initiative for a 90-Day Total Joint Arthroplasty Episode of Care*. J Arthroplasty, 2016. **31**(2): p. 343-50.
2. Nichols, C.I. and J.G. Vose, *Clinical Outcomes and Costs Within 90 Days of Primary or Revision Total Joint Arthroplasty*. J Arthroplasty, 2016. **31**(7): p. 1400-1406.e3.
3. Kurtz, S., et al., *Projections of primary and revision hip and knee arthroplasty in the United States from 2005 to 2030*. J Bone Joint Surg Am, 2007. **89**(4): p. 780-5.
4. Shetty, A.A., et al., *Comparing wound complication rates following closure of hip wounds with metallic skin staples or subcuticular vicryl suture: a prospective randomised trial*. J Orthop Surg (Hong Kong), 2004. **12**(2): p. 191-3.
5. Livesey, C., et al., *Skin closure after total hip replacement: a randomised controlled trial of skin adhesive versus surgical staples*. J Bone Joint Surg Br, 2009. **91**(6): p. 725-9.
6. Wyles, C.C., et al., *The Chitranjan Ranawat Award: Running Subcuticular Closure Enables the Most Robust Perfusion After TKA: A Randomized Clinical Trial*. Clin Orthop Relat Res, 2016. **474**(1): p. 47-56.
7. Khan, R.J., et al., *A comparison of three methods of wound closure following arthroplasty: a prospective, randomised, controlled trial*. J Bone Joint Surg Br, 2006. **88**(2): p. 238-42.
8. Campbell, A.L., et al., *Superficial wound closure complications with barbed sutures following knee arthroplasty*. J Arthroplasty, 2014. **29**(5): p. 966-9.
9. Gililand, J.M., et al., *Perioperative closure-related complication rates and cost analysis of barbed suture for closure in TKA*. Clin Orthop Relat Res, 2012. **470**(1): p. 125-9.

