Wound closure techniques have been well-studied in a variety of surgical specialties, however, the level of evidence reported in the literature in regards to TJA is scarce. Thus, the current randomized, control trial study aims to investigate the perioperative outcomes and costs of various wound closure techniques including zipper technology, monocryl suture plus Dermabond, and polyester plus Dermabond wound closure techniques. The zipper wound technology is a new wound closure device that is an alternative to the commonly used conventional staples and sutures. The device acts like a scaffold to stabilize the adjacent sides of a wound in order to minimize forces that can disrupt normal healing of the skin. Monocryl suture plus Dermabond is a commonly used combination of wound closure techniques today. Finally, the polyester plus Dermabond closure techniques combines the OCA topical skin adhesive with a flexible, self-adhesive polyester mesh that has proven to reduce wound closure times and have a significant greater skin holding strength than skin staples or subcuticular sutures in one study. Although there have been prior studies measuring the efficacy of these closure techniques individually, none have compared these three particular ones following TJA. Furthermore, in order to provide the highest level of evidence as possible for the study, it will be conducted in a randomized fashion.

CONFIDENTIAL

This material is the property of the NYU School of Medicine and Langone Medical Center. Do not disclose or use except as authorized in writing by the study sponsor

The hypothesis of the study is that there will be reduced complications rates, improved outcomes, and overall cost reduction for the zipper technology versus the other two closure techniques.

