1.3 Clinical Data to Date

A recent meta-analysis[22] compared this surgical zipper technique to conventional sutures in closing surgical wounds based on 4 randomized, control trials. The study showed that there was a similar incidence of postoperative complications, less time for incision closure, less cost for personnel involved in the procedure as well as total operating times, and higher levels of patient comfort for the zipper technique cohort.

Research Risks and Benefits

Risks

There are low associated risks with all three closure techniques. Commonly documented complications associated with all closure techniques include infection, abscess formation, hematoma formation, dehiscence, prolonged discharge, and allergic reactions. These risks are minimal overall with minimal risk differences between each technique. Thus, at worst, there will be minimal change in risks whether patients are randomized or have the option to choose a specific technique.

Benefits

There may be no direct benefit from agreeing to participate in this study. It is hoped that the knowledge gained will be of benefit to others in the future.

1.4 Primary and secondary objectives:

Primary objective: to identify the rate of complications associated with each type of wound closure technique. Some of these complications will include infection, abscess formation, dehiscence, prolonged drainage, allergic reactions, among others.

Secondary objective: to determine the cost effectiveness of each of these wound closure techniques, which will be calculated by the differences in supply costs, total lengths of operation, and postoperative complications.

CONFIDENTIAL

This material is the property of the NYU School of Medicine and Langone Medical Center. Do not disclose or use except as authorized in writing by the study sponsor

2 Study Design

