2.3 Secondary Study Endpoints

Cost effectiveness will be determined by the increased LOS, readmissions, cost of supplies, and differences in wound closure time between the differences in wound closure techniques. Each of these variables will be calculated based on the associated hospital costs and analyzed to determine the most cost effective wound closure technique.

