Perioperative costs – cost of supplies, time to wound closure, operative times, length of stay, readmissions		X	X			
Randomization		X				
Study treatment dispensation		X				
Subject Survey – VAS score, HWES score			X	X	X	X

5 Statistical Plan

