5.2 Statistical Methods

Data on patient baseline characteristics, procedural characteristics, perioperative outcomes, functional outcomes, and costs will be collected. Single variable and multivariate statistical analysis will be performed to assess the aforementioned data points. Dichotomous data outcomes will be analyzed using odd ratios and chi-squared tests while continuous data points will be analyzed using Student t-tests. Each complication will be documented for every patient. The rates of complication will be analyzed individually for each technique, and risk ratios will be conducted between techniques to determine which technique has the lowest risk of developing a complication. Complications include infection, abscess formation, dehiscence, prolonged drainage, allergic reactions, among others. Cost effectiveness will be determined by the differences in quality metrics such as LOS, readmissions, cost of supplies, and differences in wound closure time between the different wound closure techniques. Each of these variables will be calculated based on the associated hospital costs and analyzed to determine the most cost effective wound closure technique.

CONFIDENTIAL

This material is the property of the NYU School of Medicine and Langone Medical Center. Do not disclose or use except as authorized in writing by the study sponsor

6 Safety and Adverse Events

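### The cost-effectiveness endpoint ranks techniques on hospital cost alone, its components differ from those in the objective, and Section 10.2 contradicts the use of supply-cost differences

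*Combined protocol and SAP*

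**What the plan says.** The hypothesis at the end of the introduction includes "overall cost reduction for the zipper technology versus the other two closure techniques". Four further places describe how cost is to be handled.

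- **Section 1.4 (secondary objective):** cost effectiveness is "calculated by the differences in supply costs, total lengths of operation, and postoperative complications".
- **Section 2.3 (secondary endpoint):** "Cost effectiveness will be determined by the increased LOS, readmissions, cost of supplies, and differences in wound closure time".
- **Section 5.2 (statistical methods):** "Cost effectiveness will be determined by the differences in quality metrics such as LOS, readmissions, cost of supplies, and differences in wound closure time". The next sentence gives the valuation and the decision: "Each of these variables will be calculated based on the associated hospital costs and analyzed to determine the most cost effective wound closure technique".
- **Section 4 (schedule table):** the perioperative cost row collects "cost of supplies, time to wound closure, operative times, length of stay, readmissions". A separate row records complications before discharge and at each of the three postoperative visits.

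Section 10.2, explaining why the study needs no funding, says that all three techniques are in regular use and that "there are no supply cost differences between them".

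**The concern.** A cost-effectiveness claim needs a cost, an effect, and a rule for combining them. In the endpoint and analysis sections every named component is turned into a cost. Complications, which are the primary outcome and an input under Section 1.4, are absent from both lists. A complication then counts only through any extra stay or readmission it causes. Some listed complications, such as prolonged drainage or an allergic reaction, could occur without either.

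At stake is the secondary conclusion. A technique that is cheaper but has more complications could be reported as the most cost effective, which conflicts with the intent of Section 1.4. Two analysts working from different sections would also compute different quantities, and Section 10.2 leaves it unclear whether supply cost is a live component.

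**Working it through.** The plan states no figure for this endpoint, so there is nothing to reproduce. The check is a comparison of the text, followed by the algebra of the definition.

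**Step 1. Component lists side by side.**

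| Component | Section 1.4 | Sections 2.3 and 5.2 | Collected (Section 4) |
|---|---|---|---|
| Supplies | yes | yes | yes |
| Total operation length | yes | no | yes |
| Closure time | no | yes | yes |
| Length of stay | no | yes | yes |
| Readmissions | no | yes | yes |
| Complications | yes | no | yes (own row) |

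Only supplies appear in both definitions, and that is the component Section 10.2 says does not differ.

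**Step 2. What the endpoint ranks.** For two techniques, write Δ for the difference in means and c for a unit cost. Sections 2.3 and 5.2 give

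ΔC = ΔSupplies + c(time) × ΔClosure time + c(stay) × ΔLOS + c(readmission) × ΔReadmissions.

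The difference in complication rate, ΔE, is not in the expression. If extra complications in one arm leave LOS and readmissions unchanged, they add 0 to ΔC and the ranking ignores them.

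**Step 3. Where that matters.** There are four combinations:

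- cheaper, fewer complications: dominant, and no ratio is needed;
- dearer, more complications: dominated, and no ratio is needed;
- cheaper, more complications: the plan names it best without weighing the harm;
- dearer, fewer complications: the plan ranks it below without weighing the benefit.

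In two of the four, ranking on ΔC agrees with a cost-effectiveness ranking. In the other two the documents give no effect measure, ratio, net benefit or threshold.

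**Step 4. Section 10.2.** If the clause is true, ΔSupplies = 0 for every pair and the component is uninformative. The remaining three terms in Step 2 are unaffected. If it is untrue, Section 10.2 needs correcting. The documents do not show which.

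**Step 5. Overlap between the lists.** Closure is part of the operation. If closure takes d minutes longer in one arm and the rest of the operation is equal, pricing one time measure contributes c × d. Pricing both contributes c × d + c × d = 2 × c × d. Only an analyst who merged the lists would do this; no section asks for it.

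**Step 6. Could equal complication rates be assumed?** Section 5.1 gives 200 patients at 1:1:1, so 200/3 ≈ 66 per arm. Alpha and rates are not stated, so two-sided 0.05 and the rates below are assumptions. The usual normal approximation is

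power = Φ{[|p1 − p2| − 1.96 × √(2p̄(1 − p̄)/n)] / √[(p1(1 − p1) + p2(1 − p2))/n]}.

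For 20% versus 4.2%, p̄ = 0.121 and the two standard errors are 0.0568 and 0.0551. Then (0.158 − 1.96 × 0.0568)/0.0551 ≈ 0.85, and power ≈ 80%. From 15%, the comparator must be about 1.6%. From 10%, no reduction reaches 80%. Finding no difference would therefore be weak evidence of equal complication rates.

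**The case against.** The strongest defence is that Section 1.4 does name complications, that Sections 2.2 and 5.2 compare complication rates between techniques, and that the Section 5.2 list is introduced as examples. On that reading, length of stay and readmissions are how complications enter the costs, and a reader can set the two results side by side. Section 3.2 also describes the three techniques as having comparable complication rates, in which case a cost ranking would be enough.

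Part of this stands. An effect measure is not missing from the whole document: complications are in the objective and are collected, but have no stated role in the endpoint or analysis. The rest does not answer the point. Section 5.2 still turns each component into hospital cost before choosing a technique. Comparable rates cannot be assumed in a trial whose hypothesis is that the zipper reduces complications, nor shown reliably at this size (Step 6).

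A reader might infer several stronger things that the documents do not support:

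- **That time is double counted by design.** No single definition prices both closure time and operation length. Collecting both is not pricing both. This is a risk from inconsistent lists.
- **That with supplies at zero the ranking rests only on closure time.** Length of stay and readmissions remain.
- **That Section 10.2 hides a true price difference.** It sets no costing rule, and no document shows that prices differ.
- **That no cost-effectiveness conclusion is possible.** A technique with lower cost and fewer complications would dominate without any ratio.

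**Conclusion.** The point holds as a defect of definition in a secondary endpoint; no bias has been demonstrated. Three things are established from the text. The endpoint and analysis sections rank on hospital cost and give complications no weight beyond any added stay or readmission. The objective and the endpoint share only one component, supplies. Section 10.2 contradicts the use of supply-cost differences in Section 1.4; its funding context does not remove the conflict, because the clause compares the techniques with each other.

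The size is structural. Two of the four cost and complication combinations have no decision rule, and the one shared component is zero if Section 10.2 is right. No monetary size can be given, because the documents state no unit costs. The conclusion assumes that some complications cause neither a longer stay nor a readmission. If every complication did, part of its consequence would reach the ranking through cost, but still with no stated value for avoiding it.

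**What to change.** 1. Use one component list in Sections 1.4, 2.3 and 5.2. Cost operating-room time once, as closure time or operative time but not both, and say which. Cost supplies at the recorded hospital cost.
2. Name complications as the effect. Report the mean cost difference per patient between arms with a confidence interval, beside the difference in complication rate. Where neither technique dominates, add cost per complication avoided.
3. If the sponsor does not want step 2, call the result a cost comparison and remove the claim to identify the most cost-effective technique.
4. Verify the supply-cost clause in Section 10.2. Reconcile it with Sections 1.4, 2.3 and 5.2, or limit it to the statement about study funding. Changing this clause alone would alter no result.

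The cost is wording and slightly more analysis. Complications and cost items are already collected under Section 4, so no extra patients or visits are needed. The drawback is that cost per complication avoided will have a wide interval if complication rates are similar, which is a reason to show the two differences side by side.
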